7.3 Dose Modifications

Dose modifications will not be made in this study. If a subject has an intolerable adverse event or side effects related to the study treatment, the drug will be discontinued and the subject will be removed from the protocol. Follow up outcome data will still be collected to allow for intent-to-treat analysis.

7.4 Supportive Care

All supportive measures consistent with optimal patient care will be given throughout the study.

7.5 Duration of Therapy

Treatment will be discontinued within 24 hours of the subject's completion of the bladder management protocol with return of normal bladder function (2 consecutive voids with PVR less than 200mL) or requirement of IUC re-insertion for urinary retention. The maximum number of doses (days) of treatment is 14. If ongoing urinary retention is present, further management

will be deferred to the treating physician team. This sometimes involves initiation of a short course of alpha-blockers in conjunction with IUC, followed by a spontaneous voiding trial.

8.0 STUDY PARAMETERS

Component	Description	Timing	Contact points
Pre-screening for eligibility	The electronic medical	After the patient is	Study team
	records of prospective	scheduled in the	member
	subjects will be pre-	general surgery clinic,	
	screening for eligibility	prior to actual	
	by a study team	appointment.	
	member.		
	If the patient is eligible	At initial or subsequent	Surgeon,
	based on pre-	pre-operative general	resident, nurse
Invitation to participate	screening, the patient	surgery clinic	practitioner, or
in study	will be informed about	appointment	study team
in study	the study and asked		member
	about interest in		
	participating.		
	If the patient is eligible	Either initial pre-	Surgeon,
	for the study, he/she	operative clinic visit, or	resident, or study
	will be given a copy of	subsequent pre-	team member
Informed consent	the informed consent	operative clinic visit if	
	and the informed	scheduled more than 1	
	consent process will	week prior to the date	
	occur.	of surgery	
	The Eligibility Checklist	At initial or subsequent	Study team
	will be completed by a	pre-operative general	member
	study team member	surgery clinic	
Formal screening for eligibility	with the patient.	appointment	
	Includes pregnancy test		
	in women of		
	childbearing age and		
	potential.		
Enrollment	Enrollment in the study	After informed consent	Study team
	and registration.	process at preoperative	member
		clinic visit.	
	Validated survey of	Pre-operative clinic	Study team
IPSS Survey (R)	lower urinary tract	visit, after enrollment	member
	symptoms to be		
	completed by the		
	subject		

Component	Description	Timing	Contact points
Urinary history questionnaire (R)	Short questionnaire (3 questions) regarding history of urinary retention and prior urinary tract surgery or procedures	Pre-operative clinic visit, after enrollment	Study team member
Randomization	Random allocation by the PRC to either the tamsulosin group or the placebo group	Preoperative clinic visit, after enrollment.	PRC
Reminder phone call (R)	Phone call or text message from study personnel to subject on Study day 1 to remind subject to start taking the drug/placebo	Study day 1	Study team member
Pre-operative treatment with study drug (R)	Dosing of tamsulosin or placebo as described in section 7.1	Study days 1-7	Subject to self- administer at home
Screening for adverse events, time 1 of 3	Study personnel will ask subject about treatment-emergent adverse events occurring during the preoperative phase of intervention	Study day 8, pre or post operatively	Study team member
Operation (SOC)	Elective inpatient complex intra- abdominal surgery as scheduled	Study day 8	Surgeon
Post-operative treatment with study drug (R)	Dosing of tamsulosin or placebo as described in section 7.1	Study days 8-14, or discontinued prior to day 14 based on completion of bladder management protocol or re-insertion of IUC	Administered by subject's RN
Bladder management protocol (see appendix) (SOC)	Monitoring of bladder volume via supra-pubic ultrasound, measurement of post- void residual volume, intermittent catheterization as needed	Postoperatively, while inpatient (Days 8-14)	Subject's RN
Screening for adverse events, time 2 of 3	Study personnel will perform review of the	From day of surgery until 48 hours after	Study team member

Component	Description	Timing	Contact points
	EMR to abstract AEs	completing the	
	occurring during the	intervention	
	postoperative phase of		
	intervention		
	Telephone call to	30-40 days after	Study team
Final study visit (R)	subject by study team personnel	surgery	member
	Study personnel will	30-40 days after	Study team
	ask subject about	surgery via telephone	member
	treatment-emergent	call, will be combined	
Screening for adverse	adverse events	with inquiry about UTI	
events, time 3 of 3 (R)	occurring during the	(see below)	
	post-intervention		
	phase of trial (up to 30		
	days after surgery)		
	Telephone call to	30-40 days after	Study team
Inquiry about diagnosis of UTI (R)	patient 30 days after	surgery via telephone	member
	surgery to inquire	call (will be combined	
	about whether the	with above phone	
	patient has been	call)/chart review	
	treated for a UTI since		
	surgery; chart review		
	for UTI diagnosis within		
	our institutional EMR		

9.0 DRUG FORMULATION AND PROCUREMENT

9.1 Tamsulosin hydrochloride (NDC 0597-0058-01)

- 9.1.1 Other names: FLOMAX
- 9.1.2 Classification: alpha_{1A} adrenoceptor antagonist
- 9.1.3 Mode of Action: Tamsulosin works by blocking alpha_{1A} adrenergic receptors in the prostate, prostatic urethra, and bladder neck, which results in relaxation of the smooth muscles in the bladder neck and prostate, thereby reducing bladder outlet obstruction.
- 9.1.4 Storage and stability

Stored at 25 degrees Celsius (77 degrees F); excursions permitted to 15 degrees C to 30 degrees C (59 degrees F to 86 degrees F)

9.1.5 Dose specifics: 0.4mg orally dosed one time per day, 30 minutes after a meal, in the evening

- 9.1.6 Preparation: capsule
- 9.1.7 Route of administration: orally; capsules should not be crushed, chewed, or opened
- 9.1.8 Incompatibilities
 - 9.1.8.1 Other alpha-adrenergic blockers

Per package insert: "The pharmacokinetic and pharmacodynamic interactions between FLOMAX capsules and other alpha-adrenergic blocking agents have not been determined. However, interactions may be expected and FLOMAX capsules should NOT be used in combination with other alpha-adrenergic blocking agents." Patients taking concomitant alpha blockers (including verapamil, which has alpha blockade action at therapeutic doses) will be excluded from the study.

9.1.8.2 Cimetidine

Per package insert: "The pharmacokinetic interaction between cimetidine and FLOMAX capsules was investigated. The results indicate significant changes in tamsulosin HCl clearance (26% decrease) and AUC (44% increase). Therefore, FLOMAX capsules should be used with caution in combination with cimetidine, particularly at doses higher than 0.4 mg." Patients taking cimetidine will still be eligible for the study, but will be notified about potential increased risk of side effects.

9.1.8.3 Warfarin

Per package insert: "A definitive drug-drug interaction study between tamsulosin hydrochloride and warfarin was not conducted. Results from limited *in vitro* and *in vivo* studies are inconclusive. Therefore, caution should be exercised with concomitant administration of warfarin and FLOMAX capsules." We will exclude patients taking warfarin.

9.1.8.4 Strong inhibitors of CYP3A4 (boceprevir, clarithromycin, conivaptan, grapefruit juice, indinavir, itraconazole, ketoconazole, lopinavir, nefazodone, nelfinavir, posaconazole, ritonavir, saquinavir, telaprevir, telithromycin, voriconazole) and CYP2D6 (bupropion, fluoxetine, paroxetine, quinidine)

It is recommended that doses higher than 0.4mg daily should not be used in combination with strong inhibitors of CYP3A4 or CYP2D6 and that caution should be exercised when using tamsulosin in combination with such drugs. Studies have demonstrated an increased AUC and C_{max} when tamsulosin is taken in combination with strong inhibitors of CYP2D6 or CYP3A4, but these increases have been shown to still fall equivalently or below the higher U.S. dosage of 0.8mg daily. One study specifically examining clinical effects (i.e. orthostasis) of

concomitant tamsulosin/paroxetine and tamsulosin/ketoconazole found no significant clinical effect of these medications being co-administered. Patients taking strong inhibitors of CYP3A4 or CYP2D6 will not be excluded from the study, however they will be advised about potential increased risk of side effects.

- 9.1.9 Availability: commercially available
- 9.1.10 Side effects (reported in package insert; data derived from two U.S. clinical trials (US92-03A and US93-01)^{7,8}:

	Tamsulosin 0.4mg	Placebo
	(n=502)	(n=493)
Body as whole		
Headache	97 (19.3%)	99 (20.1%)
Infection	45 (9.0%)	37 (7.5%)
Asthenia	39 (7.8%)	27 (5.5%)
Back pain	35 (7.0%)	27 (5.5%)
Chest pain	20 (4.0%)	18 (3.7%)
Nervous System		
Dizziness	75 (14.9%)	50 (10.1%)
Somnolence	15 (3.0%)	8 (1.6%)
Insomnia	12 (2.4%)	3 (0.6%)
Libido decreased	5 (1.0%)	6 (1.2%)
Respiratory System		
Rhinitis	66 (13.1%)	41 (8.3%)
Pharyngitis	29 (5.8%)	23 (4.7%)
Cough increased	17 (3.4%)	12 (2.4%)
Sinusitis	11 (2.2%)	8 (1.6%)
Digestive System		
Diarrhea	31 (6.2%)	22 (4.5%)
Nausea	13 (2.6%)	16 (3.2%)
Tooth disorder	6 (1.2%)	7 (1.4%)
Urogenital System		
Abnormal ejaculation	42 (8.4%)	1 (0.2%)
Special Senses		
Blurred vision	1 (0.2%)	2 (0.4%)

Table reproduced (with modification) from Flomax package insert.

In the two U.S. clinical trials referenced above, symptomatic postural hypotension occurred in 0.2% of men treated with tamsulosin 0.4mg vs. no patients in the placebo groups. Syncope occurred in 0.2% of men treated with tamsulosin 0.4mg vs. 0.6% in the placebo groups. Multiple testing for orthostatic hypotension was also performed in these studies, and demonstrated a 16% rate of at least one positive orthostatic test result in the tamsulosin 0.4mg subjects, vs. 11% rate in the placebo group.^{7,8}

No men in the tamsulosin 0.4mg group or placebo group discontinued treatment due to abnormal ejaculation.

In a double-blind RCT comparing tamsulosin 0.2mg to placebo in 140 women over a 4-week period, there were 2 patients out of 70 in the tamsulosin group who had dizziness and asthenia (2.9%) compared to no adverse effects reported in the placebo group.⁹

- 9.1.10.1 Incidence not known (Post-marketing experience)
 - 9.1.10.1.1 Allergic reactions including skin rash, pruritus, angioedema of tongue, lips and face, urticarial. This has been reported in patients with severe sulfa allergy, and therefore severe sulfa allergy is one of the exclusion criteria for this study.
 - 9.1.10.1.2 skin desquamation
 - 9.1.10.1.3 Priapism (probably less than 1 in 50,000 patients)
 - 9.1.10.1.4 palpitations
 - 9.1.10.1.5 hypotension
 - 9.1.10.1.6 constipation
 - 9.1.10.1.7 vomiting
 - 9.1.10.1.8 Intraoperative Floppy Iris Syndrome (IFIS): This is a clinical syndrome of a flaccid billowing iris, iris prolapse, and pupil constriction that has been described during cataract surgery and has been associated with tamsulosin. This syndrome increases the difficulty of performing cataract surgery and increases the rate of complications associated with cataract surgery.¹⁰ It has been found to occur even up to a year after discontinuation of tamsulosin, and possibly longer.¹¹ However, one prospective study evaluating outcomes after surgery in which IFIS was present found that when surgeons were aware of prior or current tamsulosin use, they were able to employ compensatory techniques resulting in a low complication rate.¹¹

9.1.11 Nursing implications

Nursing staff would administer the study medication when the patient is in the hospital.

10.0 STATISTICAL CONSIDERATIONS

10.1 Randomization and stratification

Subjects will be stratified by gender, pelvic/non-pelvic surgery, and high vs low IPSS score (which "high" defined as >=8, and "low" <=7) prior to randomization. Subjects will be randomized with a 50/50 chance of being allocated to active drug or placebo. Randomization will be performed by the Pharmaceutical Research Center, and the code sheet for randomization will be kept by the PRC. Unblinding of study team members will only occur for

interim data analysis, which will be performed between May 15 and May 30, 2016. Only subjects for who complete data collection (including 30-day postoperative outcomes) has been obtained will be unblinded at that time.

For purposes of stratification, "pelvic" operations include the following: surgery involving the rectum (colorectal anastomosis, ileo-rectal anastomosis, IPAA, proctopexy, proctocolectomy, proctectomy, LAR, and APR).

10.2 Sample size

In this study, we propose to compare a group of subjects given a placebo and a group given tamsulosin in order to prevent postoperative urinary retention. The primary endpoint is need for at least a single intermittent catheterization, treated as a binary outcome. Secondary endpoints include need for indwelling catheter replacement (binary), time until first void (continuous), number of intermittent catheterizations (numeric), post-void residual urine volumes (continuous), UTI rates (binary), and length of stay (continuous). The sample size calculation is based on the primary endpoint. We will employ a two-tailed, two sample test for equality of proportions (chi-squared or Fisher's exact) at a significance level of 0.05 (equivalent to one-tailed alpha of 0.025) in order to compare urinary retention rates as measured by our primary outcome. Based on pilot data and information from the literature, we anticipate that 30% of the placebo group will experience urinary retention, and that the tamsulosin group will see a 50% reduction to a 15% urinary retention rate. In order to achieve at least 80% power for detecting a significant group difference, we will need 134 subjects included in each study arm, or a total of 268 subjects. However, to provide for a 10% drop out rate, we would need to plan to enroll 147 subjects in each arm, yielding an enrollment goal of 294 subjects.

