10.5 Estimated accrual rate / study duration

The estimated sample size needed to achieve the pre-specified statistical significance and power is a total of 268 subjects (134 subjects in each arm). Subjects that withdraw from the study prior to surgery will be replaced. We estimate that there will be a 10% drop-out rate, and therefore the enrollment goal to account for drop-outs is estimated to be 294 subjects (147 in each arm) in order to achieve an actual sample size of 268 subjects. We initially predicted that we would need to replace subjects that received epidural anesthesia, but the interim analysis showed no significant difference in response between epidural and non-epidural patients.

The estimated accrual rate is approximately 1-2 subjects per week. In order to enroll a total of 294 subjects, this would take approximately 147-294 weeks, or 2.8-5.7 years. After enrollment of the final subject, data collection will continue for 30 days beyond that subject's date of surgery. Expected study duration is approximately 3-6 years from the time that enrollment begins.

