10.9 Maximum number of subjects

We have allowed for a 10% drop out in our enrollment goal calculation. If, however, drop-out rate exceeds the allowed 10%, we will enroll additional subjects to maintain 80% power at a 0.05 significance level. As a contingency plan, the maximum number of subjects we will enroll will be based on a 30% drop out rate. This would yield a maximum number of subjects in each arm of 174, or a total maximum enrollment of 348 subjects.

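### Enrolment is inflated by (1 + d) instead of 1/(1 − d), so 294 and 348 subjects do not leave 268 after 10% and 30% drop-out; the 348 cap supports about 23%

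*Combined protocol and SAP*

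**What the plan says.** Section 10.2 bases the sample size on a "two-tailed, two sample test for equality of proportions" at two-sided 0.05, using chi-squared or Fisher's exact, with retention of 30% on placebo and 15% on tamsulosin. For at least 80% power it asks for 134 per arm, 268 in total. It then adds the drop-out allowance: "to provide for a 10% drop out rate, we would need to plan to enroll 147 subjects in each arm", for an enrolment goal of 294.

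Section 10.5 says what that goal should deliver: "294 subjects (147 in each arm) in order to achieve an actual sample size of 268 subjects".

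Section 10.9 covers drop-out above 10%. More subjects will then be enrolled so that power stays at 80% at the 0.05 level, and "the maximum number of subjects we will enroll will be based on a 30% drop out rate". It continues: "This would yield a maximum number of subjects in each arm of 174", or 348 overall. No section states the inflation formula.

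**The concern.** A 10% drop-out rate means that 10% of the subjects enrolled are lost, so the number retained is the number enrolled times 0.90. The plan appears instead to have added 10% (and 30%) of the required number. That always gives too few, and the error grows with the rate: it hardly shows at 10% but is substantial at 30%.

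Two statements depend on these figures. Section 10.5 claims that 294 yields 268. Section 10.9 offers a ceiling that is supposed to protect 80% power up to 30% drop-out. The ceiling limits the trial only when drop-out is high, and at the 30% rate for which it was set it leaves too few subjects.

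**Working it through.** **Inputs.** Placebo 30%, tamsulosin 15%, two-sided alpha 0.05, power 80%, 134 per arm (sections 10.2 to 10.4); 1:1 allocation (10.1); 10% drop-out with 147 per arm (10.2, 10.5); 30% drop-out with 174 per arm (10.9).

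**1. Reproduce 134.** The mean rate is (0.30 + 0.15)/2 = 0.225. Without continuity correction:

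n = [1.960 √(2 × 0.225 × 0.775) + 0.842 √(0.30 × 0.70 + 0.15 × 0.85)]² / 0.15² = 120.5, so 121 per arm.

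With continuity correction:

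n′ = (120.47/4) × [1 + √(1 + 4/(120.47 × 0.15))]² = 133.5, so **134 per arm**.

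The plan's figure is therefore reproduced by the continuity-corrected formula.

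**2. Reproduce 147 and 174.**
- 134 × 1.10 = 147.4, stated as 147.
- 134 × 1.30 = 174.2, stated as 174.

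Both match n × (1 + d), rounded to the nearest whole number.

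**3. Enrolment needed to retain 134 per arm, n/(1 − d).**
- 10%: 134/0.90 = 148.9, so 149 per arm, 298 in total (4 more than 294).
- 30%: 134/0.70 = 191.4, so 192 per arm, 384 in total (36 more than 348).

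**4. What the stated enrolments leave.**
- 294 × 0.90 = 264.6 (132.3 per arm), which is 3.4 below 268.
- 348 × 0.70 = 243.6 (121.8 per arm), which is 24.4 below 268 (24.4/268 = 9%).

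**5. Largest drop-out that still leaves 268.**
- 1 − 268/294 = 8.8%.
- 1 − 268/348 = 23.0%.

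**6. Exact power, 30% against 15%, two-sided 0.05, by full enumeration of the two binomials.**

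| Per arm | Fisher | Corrected chi-squared | Uncorrected chi-squared |
|---|---|---|---|
| 134 (required) | 80.6% | 80.6% | 84.7% |
| 132 (294 at 10%) | 80.5% | 79.98% | 84.1% |
| 122 (348 at 30%) | 76.4% | 76.3% | 81.3% |

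**The case against.** Five points can be made for the plan.

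- **The 10% gap is negligible.** This stands. It is about three subjects, power stays at about 80% or better, and 294 is not a hard limit, because section 10.9 permits more enrolment and sections 5.6.3, 5.6.6 and 10.5 replace subjects who withdraw before surgery. Replacement cannot repair the 30% case if replacements count toward the 348, as a cap on total enrolment implies.
- **The cap works over most of its range.** Also true: 348 leaves at least 268 for any drop-out up to 23.0%. It falls short between there and the 30% for which it was set.
- **An uncorrected chi-squared keeps 81.3% power at 30%.** True. But the plan allows either chi-squared or Fisher's exact without choosing, and the formula that gives 134 is the corrected one. On that basis power is 76.3%.
- **Section 10.9 promises 80% power and does not repeat 268.** Correct, but section 10.2 makes 134 per arm the number needed for that power.
- **Drop-outs may stay in the intention-to-treat analysis.** Sections 5.6.3 and 7.3 keep collecting outcomes after discontinuation, so the loss of evaluable subjects could be smaller than the drop-out rate. This is the strongest objection, and it makes 243.6 a worst case for numbers. Yet section 10.5 itself treats drop-outs as lost from the actual sample size. Nor would keeping them necessarily protect power. If all 174 per arm were analysed and the 30% who dropped out of the tamsulosin arm had the placebo rate, that arm's rate would be 0.70 × 15% + 0.30 × 30% = 19.5%. Exact power would then be 57.8% (Fisher or corrected) or 62.3% (uncorrected). That is an illustrative extreme, because some of these subjects will have taken part of the course.

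**Conclusion.** The concern holds. Both enrolment figures come from multiplying by 1 + d, and neither delivers what is claimed for it. The 294 figure is a rounding-scale error with no practical effect on power. The 348 cap is materially short: at 30% drop-out it leaves about 244 evaluable subjects, and power is about 76% on the basis that produced 134.

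This rests on three assumptions: drop-outs contribute no primary outcome, as section 10.5 treats them; replacements count toward the maximum; and the test is two-sided at 0.05, as sections 10.2 and 10.3 state. The loss of 80% power depends on the test chosen; the shortfall against 268 does not. The basic design is sound, but a stated guarantee is wrong and should be corrected.

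**What to change.** Restate the tolerances in sections 10.2, 10.5 and 10.9: 294 leaves 268 subjects at drop-out up to 8.8%, and 348 at drop-out up to 23.0%. Add that at 30% drop-out the cap leaves about 244 evaluable subjects, with about 76% power under Fisher's or the corrected test and 81% under the uncorrected chi-squared. State the formula n/(1 − d), and say whether drop-out here means a missing primary outcome or only stopping study drug. This costs wording only, although the stated tolerance becomes less favourable.

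If the sponsor prefers to keep 10% and 30%, the matching enrolments are 298 and 384. That raises the ceiling by 36 subjects and requires the accrual estimate in section 10.5 to be redone. At one to two subjects per week, 298 takes 149 to 298 weeks against the present 147 to 294, and a full 384 would take 192 to 384 weeks.

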10.3 Error levels

Two-sided type I error level is set at 0.05, and type II error level is 0.20.

10.4 Differences to be detected for comparative studies

Based on institutional urinary retention rates and information from the literature, we anticipate that 30% of the placebo group will experience urinary retention, and that the tamsulosin group will see a 50% reduction to a 15% urinary retention rate. This is the prespecified difference in the primary outcome that the study is designed to detect at a two-tailed significance level of 0.05 and power of 80%. The secondary outcomes that will be compared include need for indwelling catheter replacement, time until first void, number of intermittent catheterizations, post-void residual urine volumes, UTI rates, and length of stay. These secondary outcomes can be thought of as more hypothesis-generating. We acknowledge that we may not be powered to achieve statistical significance for our secondary outcome measures.

10.5 Estimated accrual rate / study duration

The estimated sample size needed to achieve the pre-specified statistical significance and power is a total of 268 subjects (134 subjects in each arm). Subjects that withdraw from the study prior to surgery will be replaced. We estimate that there will be a 10% drop-out rate, and therefore the enrollment goal to account for drop-outs is estimated to be 294 subjects (147 in each arm) in order to achieve an actual sample size of 268 subjects. We initially predicted that we would need to replace subjects that received epidural anesthesia, but the interim analysis showed no significant difference in response between epidural and non-epidural patients.

The estimated accrual rate is approximately 1-2 subjects per week. In order to enroll a total of 294 subjects, this would take approximately 147-294 weeks, or 2.8-5.7 years. After enrollment of the final subject, data collection will continue for 30 days beyond that subject's date of surgery. Expected study duration is approximately 3-6 years from the time that enrollment begins.

